## 5.8 Subject Death

### 5.8.1 Procedure for recording and reporting Subject Death

The investigator will document and report all subject deaths to the sponsor immediately but no later than 72 hours after becoming aware of the event.

Should death occur, the investigator should record the information in the hospital records and immediately document the information on the Death Form. By completing the form the sponsor will be notified.

Note: Refer to Table 1 ‘Data Collection’ and Appendix G ‘Data Collection Method’.  
In case of EDC failure, notify Sponsor via Fax or via [[contact]](mailto:[contact]).

Subject Death is an outcome of a serious adverse event (SAE). Death is therefore related to an SAE and all efforts to obtain the SAE details should be made and the Adverse Event form must be completed. Any supporting documentation (autopsy records, death certificates, hospitalization records) must be sent to SJM with the corresponding SAE and Death CRFs.

The subject’s death is an Early Conclusion of the subject’s participation in the investigation. Therefore, the investigator is requested to complete the Termination form.

The investigator must notify the EC, if appropriate, in accordance with national and local laws and regulations.

## 5.9 Document and data control

### 5.9.1 Traceability of documents and data

The investigator shall ensure accuracy, completeness, legibility and timeliness of the data reported to the sponsor on the electronic case report forms (eCRFs) and in all required reports. When copies of the original source document as well as print outs of original electronic source documents are retained, these shall be signed and dated by a member of the investigational site team with a statement that it is a true reproduction of the original source document.

### **5.9.2 Recording data**

Source documents shall be created and maintained by the investigational site team throughout the clinical investigation.

The data reported on the eCRFs shall be derived from, and be consistent with, source documents, and any discrepancies shall be explained in writing.

The eCRFs shall be validated by the Principal Investigator or a delegated investigator. Any change or correction to data reported shall be dated and explained if necessary. The original entry will remain available by audit trail.

### **5.9.3 Review of data**

The clinical investigation will be monitored by reviewing the eCRF approved by the investigators.

The following activities will occur:

- All eCRFs will be reviewed for completeness and accuracy after being uploaded into the database.
- The investigator (co-investigator) and/or delegate is notified regarding any missing or unclear/inconsistent data.

## **5.10 Monitoring**

On site-monitoring shall be performed during the clinical investigation in order to guarantee adherence to all applicable regulations, the Clinical Investigation Plan and the signed Clinical Study Agreement. By monitoring, the Sponsor can also verify the accuracy of data collected on the accompanying eCRFs throughout the duration of the clinical investigation.

Monitoring is necessary to ensure adequate protection of the rights and safety of human subjects involved in the clinical investigation and the quality and integrity of the data obtained during the investigation. The sponsor will at the same time assess the investigational site and study team on staffing and facilities to ensure the investigation can continue in a safe and effective fashion.

During the monitoring visits, data reported on the eCRF shall be reviewed as specified in the monitoring plan.

### **5.10.1 Designated Monitors**

Only monitors qualified by education, training and experience, which have been trained on the Clinical Investigation Plan, eCRF content, Monitoring Plan, relevant requirements and informed consent process will be allowed to perform monitoring activities during this clinical investigation. The monitor's qualifications and training will be documented by the sponsor. A list of monitors is available upon request.

### **5.10.2 Monitoring Plan**

Prior to the start of the site monitoring activities for this clinical investigation, a project specific Monitoring Plan (MP) will be created.

---

SJM CONFIDENTIAL AND PROPRIETARY

© 2012 – St. Jude Medical Cardiovascular Division: All rights reserved. No portion of this work may be reproduced in whole or in part without the express written permission of St. Jude Medical Cardiovascular Division.

Clinical Investigational Plan: EnligHTN II

At a minimum, the Monitoring Plan will include the following:

- Required activities
- Frequency of monitoring visits
- Visit Requirements
- Procedures for securing site compliance
- Monitoring report content and timelines
- Close-out procedures

The Monitoring Plan may be updated as appropriate. All revisions will be tracked.

### **5.11 Competent Authority (CA) Inspections**

The investigator and/or delegate should contact SJM immediately upon notification of a CA inspection at the site. A clinical monitor will assist the investigator and/or delegate in preparing for the inspection.

An investigator who has authority to grant access shall permit authorized CA employees, at reasonable times and in reasonable manner, to enter and inspect any establishment where devices are held (including any establishment where devices are used or where records or results are kept).

An investigator, or any person acting on behalf of such a person with respect to the investigation, shall permit authorized CA employees, at reasonable times and in reasonable manner, to inspect and copy all records relating to the investigation.

An investigator shall permit authorized CA employees to inspect and copy records that identify subjects, upon notice that CA has reason to suspect that adequate informed consent was not obtained, or that reports required to be submitted by the investigator, to the Sponsor or EC have not been submitted or are incomplete, inaccurate, false or misleading.

### **5.12 Investigation Termination**

The Sponsor reserves the right to suspend or terminate the investigation in an individual site or the entire clinical investigation for significant and documented reasons, at any stage, with appropriate written notice to the investigator.

The investigation will be terminated according to applicable regulations.

The investigator shall return all documents to the sponsor; and notify the Ethics Committee and the Competent Authority (if applicable). Follow-up for all enrolled subjects will be as per standard of care.

#### **5.12.1 Resuming the Clinical Investigation after Suspension**

The sponsor shall conclude an analysis of the reason(s) for the suspension, implement the necessary corrective actions, and decide to lift the temporary suspension. The sponsor shall inform the Principal Investigators, EC/Head of Medical Institution or regulatory authority, where

appropriate, and the regulatory authority of the rationale, providing them with the relevant data supporting this decision.

Concurrence shall be obtained from the, EC/Head of Medical Institution or regulatory authority where appropriate, before the clinical investigation resumes.

If subjects have been informed of the suspension, the Principal Investigator or authorized designee shall inform them of the reasons for resumption.

### **5.12.2 Investigation Conclusion**

The investigation will be concluded at an individual study site when:

- A Close Out visit has been performed by the Sponsor AND
- The Final report has been provided
- The final report/close-out is acknowledged by the study site's EC

## **6 Risks and Benefits of the Clinical Investigation**

### **6.1 Anticipated Adverse Events and Adverse Device Effects**

Possible adverse events associated with the renal denervation procedure include, but are not limited to:

- Acute renal injury (renal infarction, renal hematoma)
- Renal vascular injury (renal artery dissection, renal artery thrombosis, renal artery stenosis)
- Collateral tissue injury
- Malignant or accelerated hypertension
- Symptomatic hypotension
- Access site complications (arteriovenous fistula, access site thrombosis, embolisation, pseudo-aneurysm, hematoma, limb ischemia, femoral nerve injury, or seroma)
- Disseminated intravascular coagulation
- Infection (access site infection or systemic infection)
- Renal failure
- Decompensated heart failure
- Myocardial infarction
- Neurologic event (acute ischemic or hemorrhagic brain injury)
- Respiratory compromise
- Pain, including Back Pain
- Death
- Drug reactions
- Contrast allergies etc
- Bradycardia
- Vasospasms
- Vasovagal episodes

### **6.2 Steps that will be taken to control or mitigate the risks**

Every possible effort will be taken to minimize the risks, including:

---

SJM CONFIDENTIAL AND PROPRIETARY

© 2012 – St. Jude Medical Cardiovascular Division: All rights reserved. No portion of this work may be reproduced in whole or in part without the express written permission of St. Jude Medical Cardiovascular Division.

Clinical Investigational Plan: EnligHTN II

- Careful selection of experienced investigators for the clinical investigation
- Regular clinical investigation monitoring visits for each clinical investigation center
- Conduction of the clinical investigation in accordance with the Clinical Investigational Plan (CIP), all applicable laws and regulations (e.g. ISO14155:2011) and any conditions of approval imposed by the appropriate EC or applicable regulatory authorities where the clinical investigation is performed
- Preparation of the catheter and performance of the renal denervation procedure in accordance with the device IFUs.
- Catheter advancement under fluoroscopic imaging to minimize the risk of arterial damage.
- Training of Investigators both on the CIP and EnligHTN Renal Denervation procedure

## **7 Statistical Analysis**

### **7.1 Study design**

This is a post market, prospective, international, multicenter, non-randomized, single arm study of the EnligHTN™ Renal Denervation System. Approximately 500 subjects with uncontrolled hypertension will undergo renal artery ablation at approximately 40 investigational sites located internationally and will be followed up to five (5) years post procedure. Subjects will be included in one of three groups: Group A, Group B and Group C (Refer to Section 4.1 for detailed criteria for each group).

The primary objective is to evaluate a mean reduction of office Systolic Blood Pressure at six (6) months post renal denervation.

### **7.2 Sample size estimation**

The sample size of approximately 500 patients is used considering the study objectives; to observe the proportion of patients with a mean reduction of systolic blood pressure at 6 months, and peri-procedural events within 30 days post procedure. Approximately 40 Investigational sites will be invited to participate. A sample size of 500 patients will allow for each site to contribute a reasonable number of patients for this multicenter study. No formal power analysis or hypothesis test will be performed. However the data collected will be analyzed and presented using the descriptive or appropriate summary statistics.

### **7.3 Analysis Population**

All patients who have signed a Patient Informed Consent (PIC) will be considered enrolled in the study. However, Primary Analysis population will include those patients that have signed a PIC, and had the EnligHTN™ Renal Denervation System enter his/her body. The sample size of 500 are those subjects in the Primary Analysis population.

---

SJM CONFIDENTIAL AND PROPRIETARY

As Treated population will include all subjects in whom renal denervation was performed in a minimum of one renal artery per kidney (according to the Instructions for Use).

It is anticipated that there may be subjects who have enrolled in the study but are not included in the Primary Analysis population or As Treated population, such as:

- Subjects who are enrolled but do not meet baseline inclusion or exclusion criteria before the procedure; these are considered the screen failure population.
- Procedurally excluded populations will include subjects who have enrolled in the study and start the procedure, but do not have the EnligHTN™ Renal Denervation System enter his/her body, due to their anatomy, circumstances related to the procedure, or physician judgment.

Subjects that withdraw from the investigation will not be replaced in any analysis population.

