### **3.7 Procedural Exclusions**

Subjects who have been enrolled in the clinical investigation and the procedure was started but do not have the EnligHTN™ Renal Denervation System enter their body, due to their anatomy, circumstances related to the procedure, or physician judgment will be classified as procedurally excluded. The reason for the procedural exclusion will be documented on the Procedural CRF. The subject will return for a 1 month follow up visit and have a physical assessment and office blood pressure completed.

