#### 4.5 Renal Denervation Procedure

The renal nerve ablation should be performed according to the EnligHTN™ Renal Denervation System Instructions for Use (IFU).

The renal denervation procedure should always be done with the aid of fluoroscopy. With the patient under local anesthesia, an introducer sheath will be inserted into the femoral artery using the standard percutaneous technique (modified Seldinger technique). A heparin bolus of 3000 to 5000 units will then be administered intravenously or per institution's standard of care. An 8 French guiding catheter sheath will be inserted to engage each main renal artery sequentially with the angiograms recorded. Images of the left and right main renal arteries will be recorded using the non-ionic contrast and the diameter and length of each of the main renal arteries will be measured.

Prepare the patient for standard electrosurgery. Select an appropriate basket size of the Basket Renal Denervation Catheter (small size for patient with renal artery diameter between 4mm and 6mm and large size for patient with renal artery diameter between 5.5mm and 8mm) should be chosen. The Basket Renal Denervation Catheter will be inserted with the tip of the catheter positioned proximal to the bifurcation of one of the main renal arteries and the corresponding images will be recorded. The basket on the Renal Denervation Catheter will then be opened, while the impedance of each electrode on the basket will be monitored. To begin the ablation, the "START" button on the RF Generator will be pressed with the impedance, temperature and RF energy delivery monitored and recorded during the process. The investigator will decide the location(s) and number of ablation sites/lesions (4 to 8 ablation sites/lesions are recommended) in the main renal artery. When the ablation procedure is completed in this main renal artery, the basket on the Catheter will be withdrawn from the artery with the Basket Renal Denervation Catheter fully closed. Images of the renal artery using the non-ionic contrast will be recorded. Any signs of renal artery irregularities (vasospasm, stenosis or dissection) will be checked.

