#### **5.7.8 Procedure for assessing, recording and reporting adverse events, adverse device effects, serious adverse events and serious adverse device effects:**

Safety surveillance and reporting will be done for all subjects enrolled in this investigation as described below.

Safety surveillance within this investigation and the safety reporting performed by the investigator, starts as soon as the subject is enrolled in this investigation (date of signature of the informed consent). The safety surveillance and the safety reporting will continue until the last investigational visit has been performed or the subject is deceased or the subject/investigator concludes his participation into the investigation.

For the purpose of this trial, all Serious Events (regardless of relatedness) and all Adverse Device Effects (regardless of severity) will be reported via an eCRF to the sponsor. All Serious Adverse Events and all Adverse Device Effects (serious or non-serious) are to be documented and reported by the investigator to the sponsor immediately but no later than 72 hours after becoming aware of the event.

Adverse events will be assessed by the investigator for relationship to the device and to the procedures involved.

---

SJM CONFIDENTIAL AND PROPRIETARY

© 2012 – St. Jude Medical Cardiovascular Division: All rights reserved. No portion of this work may be reproduced in whole or in part without the express written permission of St. Jude Medical Cardiovascular Division.  
Clinical Investigational Plan: EnligHTN II

- Procedure related: The AE is deemed related to the procedure if it occurred during the procedure but was not directly caused by the medical device.
- Device related: The AE is deemed device related if it was directly caused by the medical device.

Investigators are responsible for promptly reporting all SAEs and ADEs to the sponsor by completing the Adverse Event form. All unresolved AEs should be followed by the investigator until resolution is reached.

Note: Refer to Table 1 ‘Data Collection’ and Appendix G ‘Data Collection Method’.  
In case of EDC failure, notify Sponsor via Fax or via [[contact]](mailto:[contact]).

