## **7.4 Data Analysis and Reporting**

In general data analysis will be performed across all subjects, as well as within each of three groups (Group A, B and C), based on Primary Analysis population unless otherwise specified.

The data collected will be presented using the appropriate summary statistics. Continuous data will be summarized using descriptive statistics (mean, number of observations, standard deviation, minimum and/or maximum values) and categorical data will be summarized using frequencies and percentages.

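### The prespecified 30-day peri-procedural event rate omits procedures that were started but stopped before any part of the EnligHTN System entered the body, even when a complication was the reason for stopping

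*Combined protocol and SAP*

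**What the plan says.** Section 7.3 limits the Primary Analysis population to consented subjects who "had the EnligHTN™ Renal Denervation System enter his/her body", and adds that "The sample size of 500 are those subjects in the Primary Analysis population". It then names enrolled subjects who fall outside both the Primary Analysis and the As Treated populations. Among them: "Procedurally excluded populations will include subjects who have enrolled in the study and start the procedure" without the System entering. The reasons allowed are anatomy, circumstances of the procedure, or the physician's judgment. Section 3.10 also leaves these subjects out of the treated target.

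Section 7.4 states that analyses are "based on Primary Analysis population unless otherwise specified". Section 7.4.2.1 defines the acute safety measure as subjects with a peri-procedural event within 30 days, divided by the number at baseline in the population concerned. It specifies no other population.

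The excluded subjects are still followed. Section 3.7 records the reason on the Procedural CRF and says: "The subject will return for a 1 month follow up visit and have a physical assessment and office blood pressure completed". Section 5.7.8 says: "Safety surveillance and reporting will be done for all subjects enrolled in this investigation as described below". Section 12.3.2 has an independent committee adjudicate all serious adverse events and adverse device effects.

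**The concern.** Section 4.5 puts several steps with their own risk ahead of the ablation catheter: femoral access, a heparin bolus, and then "An 8 French guiding catheter sheath will be inserted to engage each main renal artery sequentially with the angiograms recorded". Section 6.1 lists anticipated events that can arise at these steps, including access-site complications, renal artery dissection, vasospasm, contrast allergy and vasovagal episodes. If the operator stops because of one of them before any part of the System is in the body, the subject becomes procedurally excluded and leaves the event rate because of the event.

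The acute objective is the assessment of peri-procedural events. A rate that starts only at device entry does not describe the risk a patient takes on when the procedure starts. It is also selective: an early complication that the operator works through is counted, while the same complication that ends the procedure is not.

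**Working it through.** **Which subjects are lost.** Section 3.12 lists the System as the generator, the ablation catheter and the optional EnligHTN guiding catheter. Section 4.5 records the manufacturer of the guide, so guides of other makes are expected. Taking entry of any System component as entry of the System gives three cases:

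- EnligHTN guide already inserted, complication from guide or contrast, procedure stopped: in the Primary Analysis population, so counted.
- Guide of another make inserted, same complication, procedure stopped: procedurally excluded, not counted.
- Complication at access or heparin, before any guide, procedure stopped: procedurally excluded whichever guide was planned, not counted.

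Inclusion thus depends partly on the equipment chosen.

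**Whether such exclusions are foreseeable.** Section 4.3.5 allows the procedural angiogram to settle the anatomy when the duplex scan is inconclusive or abnormal, and 4.5 measures artery diameter during the procedure. Some unsuitable anatomy will therefore be found only after arterial access and contrast. Section 7.3 itself anticipates subjects in this category.

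**Size.** There is no figure in the plan to reproduce. Section 7.2 states "No formal power analysis or hypothesis test will be performed", and neither an event rate nor an exclusion rate is given. The 500 comes from 7.3; everything else below is an assumption.

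Let N = 500, p = event proportion in the Primary Analysis population, E = procedural exclusions, q = proportion of those with an event.

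- Planned rate: p
- Rate over all starts: (Np + Eq)/(N + E)
- Difference: E(q − p)/(N + E)

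The sign of the difference is the sign of q − p. With p = 5% (25 events):

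| E | q | Excluded subjects with event | All starts |
|---|---|---|---|
| 25 | 0% | 0 | 25/525 = 4.8% |
| 10 | 0% | 0 | 25/510 = 4.9% |
| 10 | 5% | 0.5 | 25.5/510 = 5.0% |
| 10 | 10% | 1 | 26/510 = 5.1% |
| 25 | 20% | 5 | 30/525 = 5.7% |
| 25 | 30% | 7.5 | 32.5/525 = 6.2% |

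Fractional counts are expected values. A lower event rate and a wider range for q show how far the figure could move. With p = 2% (10/500; exact 95% interval 1.0% to 3.7%):

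- 10 exclusions, 2 with an event: 12/510 = 2.4%.
- 26 exclusions (26/526, about 5% of starts), none with an event: 10/526 = 1.9%.
- 26 exclusions, half with an event: 23/526 = 4.4% (exact 95% interval 2.8% to 6.5%).

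The last case is extreme. It needs both frequent exclusions and complications as a leading cause of them.

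**The case against.** The strongest reply is that this is a descriptive, single-arm, post-market study of a device, and a device-exposed population is a defensible base for device safety. No hypothesis or threshold depends on the percentage. With 25/500 the exact 95% interval is 3.3% to 7.3%, which contains the whole 4.8% to 6.2% range. Section 7.4 says only that analyses are done this way in general, and 7.4.3 permits ad hoc analyses. All of that stands, and it limits the weight of the point. It does not remove it: an optional analysis is not a commitment, and a selection that depends on the outcome is not sampling error, so a confidence interval does not cover it.

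A reader might infer more than the documents support:

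- *That these events disappear from safety oversight.* They do not. Sections 5.7.8 and 12.3.2 keep serious events reported and adjudicated; what is missing is a prespecified summary.
- *That every event before the ablation catheter is lost.* Where the EnligHTN guide is used, events after it enters are counted.
- *That the adverse event check at 1 month is missing.* Section 3.7 does not list it, but Table 1 carries adverse events at every visit and 4.8.10 requires the check at follow-up.
- *That Group C is especially affected.* Contrast use at low eGFR does not show that those subjects are excluded more often or have uncounted events.

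**Conclusion.** The point holds as a gap in one prespecified secondary summary. Sections 7.3, 7.4 and 7.4.2.1 together leave started-then-stopped procedures out of the 30-day rate when no part of the System entered the body, and the permitted reasons for stopping do not rule out a complication.

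It would go too far to say that the planned rate must understate the risk. Under the assumptions shown, the all-starts figure runs from slightly below the planned one (4.8% against 5.0%) to moderately above it (6.2%), and it is unchanged when excluded subjects have events at the same rate as the others. It rises when complications drive the exclusions, which is when the figure matters most. The effect is probably small unless exclusions are frequent or often caused by complications. The case for the change rests on its low cost and on removing the dependence on outcome and on the choice of guide.

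**What to change.** In 7.4.2.1, add that the 30-day peri-procedural event percentage will also be reported for all subjects in whom the procedure was started, meaning the Primary Analysis population plus the procedurally excluded, with the number of starts as denominator. Show it beside the Primary Analysis rate. Define the start once, for example as arterial access, because neither 3.7 nor 7.3 says when a procedure counts as started and sites could otherwise count differently. List each procedural exclusion with its reason from the Procedural CRF and any reported event.

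In 3.7, at most add a cross-reference to the adverse event check already in Table 1 and 4.8.10.

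The cost is a definition, a sentence, one table row and a short listing. The exclusion reason, the serious-event reports and the 1-month visit are already planned. Because 5.7.8 requires reporting of serious events and adverse device effects, the added row will rest mainly on serious events for subjects in whom no device entered; a footnote should say so. The downside is a possibly slightly less favourable figure.
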